We will use the Science of Behavior Change (SOBC) experimental medicine approach to identify, measure, and influence FoR and related cognitive mechanisms (e.g., diminished future time perspective), and determine whether change in FoR is related to change in medication adherence. We will enroll N = 100 patients within 6 weeks of first presenting to the emergency department with suspected acute coronary syndrome who reported elevated early symptoms indicative of risk of developing PTSD (threat perceptions) at the time of their emergency department visit.¹¹ In all participants, we will measure FoR using the Concerns About Recurrence Scale (which we have adapted for ACS).¹³ We will also measure future time perspective using an assay from the SOBC measures repository: the Future Time Perspective Scale,¹⁴ to test their association with FoR and nonadherence. Prior to discharge, we will randomize patients to receive a computerized cognitive-affective FoR intervention [8 sessions (30 min/session; 2/week for 4 weeks)¹³ or control task, to test whether the intervention reduces FoR. The brief intervention has successfully reduced FoR in cancer patients. It trains patients to attend away from threatening disease-related cues (e.g., looking away from the word recurrence and instead toward a neutral word such as categories) and to make benign interpretations of ambiguous, potentially disease-related information (e.g., fatigue reflects lack of sleep, not ACS recurrence). Finally, we will test whether the intervention (and/or improvement in FoR) is associated with greater electronically-measured adherence to aspirin or other heart medications, including non-aspirin antiplatelet, beta-blockers, or statins, in the 2 months after discharge.

Specific Aim 1: To measure FoR in ACS patients, and test its associations with ACS-induced PTSD, diminished future time perspective, nonadherence to medications, and lack of physical activity.

Specific Aim 2: To test whether a cognitive-affective intervention reduces FoR in ACS patients.

Specific Aim 3: To test whether patients randomized to the intervention are more adherent to aspirin in the 2 months after discharge for ACS, and secondarily, whether any intervention effect is explained by reduced FoR.

Exploratory Aim 1: We will test for off-target intervention effects on future time perspective, as well as the alternative mediation path through improvement in future time perspective.

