
Participants must meet inclusion and exclusion criteria, as specified below.

Inclusion criteria

- (1) Age 18 years or older
- (2) Fluent in English or Spanish
- (3) A diagnosis of suspected acute coronary syndrome (ACS)
- (4) Currently enrolled in the protocol titled "Testing biopsychosocial mechanisms of the posthospital syndrome [PHS] model of early rehospitalization in cardiac patients" (IRB-AAAR7350)
- (5) Previously indicated "YES" to the following question in the consent form for the separate protocol (IRB-AAAR7350) in which they are enrolled: "I am willing to be contacted about other future research projects."
- (6) Elevated Threat Perception score in emergency department (or, if not available, then elevated Recollected Threat Perception score in emergency department using a

separate post-emergency department questionnaire) flagged by automatic scoring (i.e., ≥ 8 , the upper 75% of 1,000 ACS patients in a separate sample)

- (7) Currently on a daily aspirin regimen prescribed by a doctor OR currently on a daily non-aspirin antiplatelet (e.g., Plavix), beta-blocker, statin, or anti-hypertensive regimen prescribed by a doctor
- (8) Some comfort using technology such as electronic tablets or smartphones
- (9) Time elapsed since emergency department visit at which they enrolled in the PHS study is less than 6 weeks

Exclusion criteria

- (1) Deemed unable to comply with the protocol (either self-selected or by indicating during screening that s/he could not complete all requested tasks). This includes patients with a level of cognitive impairment indicative of dementia and patients with current alcohol or substance abuse
- (2) Deemed to need immediate psychiatric intervention (that is, has to be hospitalized or have some other psychiatric intervention within 72 hours)
- (3) Unavailable for follow-up. This includes patients with a terminal noncardiovascular illness (life expectancy less than 1 year by physician report) and those who indicate they are about to leave the United States
- (4) Underwent a surgical procedure within the past 24 hours and/or is scheduled for a surgical procedure within the next 24 hours

The training sessions are administered by participants via the tablet devices twice per week for 4 weeks. The design of the training is described below separately for both conditions: intervention and control.

Cognitive-Affective Training (8 at-home sessions; 30 minutes each)

Cognitive bias modification for attention (CBM-A)

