If PTSD, FoR, or both are also associated with diminished future time perspective, patients may value future life goals (e.g., maintain long-term heart health by taking aspirin daily) less than more immediate goals (e.g., avoid distressing reminders of past trauma and future mortality), with predictable consequences for health behaviors. Behavioral economics research suggests that diminished future perspective is associated with lower medication adherence among patients with hypertension and diabetes.¹⁷ We will explore the associations among PTSD, FoR, and a measure from the SOBC measures repository that assesses time perspective; the 10-item self-reported Future Time Perspective Scale assesses the extent to which participants conceive of the future as relatively limited or open-ended.¹⁴

Medication adherence. We measure adherence to aspirin objectively using eCAPS (Information Mediary Corp., Ottawa, Canada). Medication bottles with these special caps automatically record the date and time of bottle openings. Medication adherence across a unit of time (e.g., 1 week, 1 month) is computed as the proportion of days that participants took the correct number of aspirin pills. If patients are taking aspirin and other heart medications (i.e., non-aspirin antiplatelets, beta-blockers, statins, or antihypertensives), then the aspirin will be the heart medication they will place in the eCAP bottle to be monitored. However, if patients are taking other heart medications (i.e., non-aspirin antiplatelets, beta-blockers, statins, or antihypertensives) but *not* aspirin, then they will choose which one medication (either a non-aspirin antiplatelet, beta-blocker, statin, or antihypertensive) to put in the eCAP bottle to be monitored.

Threat Perceptions. In a separate protocol we measure perceptions of threat, which are very early indicators of PTSD symptoms at the emergency department.¹¹ This measure is used as part of the eligibility criteria (see above).

Context sensitivity. We measure participants’ ability to identify information about stressful situations that is helpful for the successful and flexible regulation of distress. The Context Sensitivity Index (CSI) presents hypothetical scenarios and asks participants to answer questions about them (e.g., “How much control do you have over what happens next?”).¹²

3. Statistical Procedures

Analysis Plan

Specific Aim 1.

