To measure FoR in ACS patients, and test its associations with ACS-induced PTSD, diminished future time perspective, and nonadherence to medications.

We will test the extent to which the hypothesized measures of the behavior change mechanisms in question (FoR, future time perspective) are intercorrelated in ACS patients with elevated acute stress symptoms. First, to test convergent validity, we will assess zero-order correlations among these measures. Specifically, we predict that—across both groups at Time 1 before the intervention—higher FoR will be associated with lower future time perspective (i.e., lower FTPS). Second, we will test whether higher FoR is associated with higher threat perception symptoms and overall lower proportion of days adherent to aspirin. Third, due to the within-subjects design, we will also assess test-retest reliability from Time 1 to 2, both across and within groups. In this way we will ensure that we have valid and reliable measures of our proposed mechanisms of behavior change.

Specific Aim 2.

To test whether a cognitive-affective intervention reduces FoR in ACS patients.

We will conduct a univariate ANOVA to assess the effect of the four-week intervention on pre-to-post change in FoR, the proposed target mechanism. Prior intervention research in cancer patients showed a small to moderate effect size of a cognitive-affective intervention on FoR symptoms (Hedge's g for difference in health worries from pre- to post-intervention = 0.35). In separate unadjusted tests with pre-to-post change in FoR (and in an exploratory test of future time perspective) as the outcome, we will enter group (intervention, control) as the predictor. We will repeat the tests adjusting for factors that may explain variance in health behavior, including demographic information (age, sex, race, ethnicity), medical severity assessed by GRACE risk score¹⁸ and Charlson comorbidity index,¹⁹ and depressive symptoms assessed by PHQ-8 score.²⁰

Specific Aim 3.

To test whether patients randomized to the intervention are more adherent to aspirin in the 2-month monitoring period within the first several months after their suspected ACS event, and secondarily, whether any intervention effect is explained by reduced FoR.

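### Aim 1 tests fear of recurrence against threat perception without separating scores taken in the emergency department from scores recollected later, so recall coloured by current fear could raise the correlation if the two are pooled

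*Combined protocol and SAP*

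**What the plan says.** All references are to the combined protocol and SAP.

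- **Section 1 (Study Purpose and Rationale)** describes the population by early symptoms reported "at the time of their emergency department visit".
- **Section 2, Inclusion criteria, item 6** requires an elevated score from the ED. It also allows a fallback: "if not available, then elevated Recollected Threat Perception score in emergency department", obtained from a separate questionnaire given after the ED. One threshold serves both sources: "flagged by automatic scoring (i.e., ≥ 8 , the upper 75% of 1,000 ACS patients in a separate sample").
- **Section 2, Measures, Threat Perceptions** calls these perceptions ones "which are very early indicators of PTSD symptoms at the emergency department". It says the measure comes from a separate protocol and is used for eligibility. The recollected version is not mentioned there.
- **Section 3, Specific Aim 1** states that "we will test whether higher FoR is associated with higher threat perception symptoms". No score source is named.

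The plan contains no indicator of score source, no ED-only analysis, no adjustment for source and no sensitivity analysis by source. It gives neither the date of the recollected questionnaire relative to Time 1 nor the expected number of patients who will rely on it.

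**The concern.** A score taken in the ED precedes the Time 1 FoR interview, so fear measured at Time 1 cannot have altered it. A recollected score is a later self-report about the same visit. If the patient is already worried about recurrence when asked, that worry may raise the remembered threat, and the two self-reports then correlate for a reason unrelated to what was felt in the ED. A coefficient that pools both sources mixes two different associations.

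The coefficient matters within Aim 1. That aim sets out to relate FoR to PTSD induced by the cardiac event. The Measures section describes no PTSD scale, and the only PTSD-related test in the Aim 1 analysis plan is this one. Without a source flag, a reader of the results could not tell whether the recollected share was small enough to ignore.

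**Working it through.** The plan states no figure for this test. Its power statement (f = 0.35, N = 100) concerns Aim 2 only, so there is nothing to reproduce. What follows is an illustration.

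**Inputs from the documents.** N = 100 (section 2). Alpha = 0.05 (section 3, Power analysis, stated for Aim 2; taken here as two-sided for Aim 1). Cut-off of 8, described as the upper 75% of a reference sample.

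**Assumptions, because the documents are silent.** Sources are pooled. FoR is the Time 1 score. Scores are bivariate normal with equal means and variances before selection. The ED correlation is 0 and the recollected correlation is 0.5, both before selection. The recollected share p is 10%, 30% or 50%.

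**Step 1: no cut-off.** Pooled r = (1 − p) × 0 + p × 0.5 = 0.05, 0.15, 0.25. By Fisher z with standard error 1/√97, the chance of p < 0.05 is 8%, 32% and 71%. This ignores that every enrolled patient has passed the threshold.

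**Step 2: cut-off keeping the upper 75%.** Truncating a standard normal at −0.674 leaves mean 0.424 and variance 0.535. The pooled correlation is then

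r = p × 0.5 × 0.535 / √(0.535 × V),

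where V, the variance of FoR, is p × (0.75 + 0.25 × 0.535) + (1 − p) + p(1 − p) × (0.5 × 0.424)².

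- p = 10%: V = 0.992, r = 0.0267/0.729 = 0.04
- p = 30%: V = 0.975, r = 0.0802/0.722 = 0.11
- p = 50%: V = 0.953, r = 0.1337/0.714 = 0.19

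Simulation at N = 100 gives a chance of p < 0.05 of about 7 to 8%, 20 to 21% and 47%, against 5% with ED scores alone. Differences of a point between runs are simulation error.

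**Step 3: cut-off keeping only the top 25%.** The phrase about the upper 75% could also mean above the 75th percentile. Simulated rejection is then about 6 to 7%, 12% and 24%.

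**Step 4: a real ED association.** With an ED correlation of 0.2 before selection and the upper 75% kept, the ED-only value after selection is 0.2 × √0.535 / √(0.96 + 0.04 × 0.535) = 0.15. Simulated pooled r is 0.17, 0.22 and 0.26 for the three shares. Recall colouring raises r above the ED-only 0.15, but range restriction has already pulled it down, so the pooled value can lie below or above the unrestricted 0.2.

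**Step 5: a different model.** Let the recollected score equal ED threat plus b times FoR, rescaled, with b = 0.25 or 0.5, true r = 0 and the upper 75% kept. False-positive rates are 5 to 7% at a 10% share, 8 to 13% at 25% and 15 to 39% at 50%. The direction is the same and the size again depends on the share.

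**The case against.** The strongest reply is that much of this rests on silence.

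- **Timing.** A reader might infer that recollections were taken up to six weeks after the ED visit, with fear of recurrence already established. The documents do not support that. Six weeks is the limit for enrolment, not a stated window for this questionnaire. Recruitment is said to be mainly in hospital, so the recollection could follow the ED visit closely. The separate protocol, which is not available here, may fix the date. This stands: colouring of recall is a possibility, not a documented fact.
- **Pooling.** Criterion 6 is an eligibility rule, and Aim 1 does not say that recollected scores replace missing ED scores in the analysis. This stands in part: the Measures section names a single threat measure, ties it to eligibility and plans no separation, so pooling is the natural reading but still an inference.
- **Direction.** A reader might take Aim 1 as claiming that early threat leads to FoR. Its analysis plan claims only an association, within a check that the measures are valid and reliable.
- **Size.** The share and the value 0.5 are assumptions. A fallback used only for missing scores may well be rare, and at 10% the effect is slight. This stands.
- **ED scores are not clean either.** Two self-reports can share trait distress even when threat is measured in the ED. This stands, and it limits what separation by source can achieve.

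None of this supplies the missing source flag or by-source analysis.

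**Conclusion.** The concern holds as a conditional one. The plan admits two kinds of threat score, describes only one of them as the construct, and does not separate them in the Aim 1 test. If they are pooled and current fear colours recall, the correlation can be raised or created.

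Under the stated assumptions with the upper 75% kept, the chance of a significant result where the ED correlation is zero is about 8%, 20% and 47% at recollected shares of 10%, 30% and 50%. If only the top 25% is kept, it is about 7%, 12% and 24%. The figure of 71% applies only if the cut-off is ignored or if 0.5 is the correlation after selection. Net inflation over the unrestricted correlation is not assured.

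A reader might also infer that the trial's randomised results are at risk. They are not: the planned Aim 2 and Aim 3 comparisons do not use the threat score. The reach is one Aim 1 correlation, and the point is a cheap improvement rather than a flaw in the trial.

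**What to change.** - Record the source (ED or recollected) and the date of each threat score.
- Report the Aim 1 correlation between threat and FoR on ED-measured scores and on recollected scores separately, with the number of patients in each.
- Base any statement about threat at the ED visit on the ED-score result.
- Show the full-sample estimate as secondary.

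This leaves eligibility and the questionnaires unchanged. It costs one flag, one date and one further line of analysis.

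The downside is precision in the ED-only estimate. The smallest correlation detectable with 80% power is tanh(2.80/√(n − 3)): tanh(2.80/√97) = 0.28 at n = 100, and tanh(2.80/√67) = 0.33 at n = 70, the size left if 30% of scores are recollected. The actual loss cannot be stated because the share is not given. The change removes recall bias from the ED-only result but not shared self-report or trait distress, and the report should say so.

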Exploratory Aim 2: We will test whether the intervention is associated with greater increases in physical activity relative to the control group and whether this association is mediated by changes in FoR or future time perspective.

Half of ACS patients are nonadherent to secondary prevention medications within 1 year of their ACS event, and so are at increased ACS recurrence and mortality risk.¹⁵ PTSD symptoms are associated with nonadherence after acute cardiovascular events, and our work suggests that FoR may underlie that association. This will be the first study to identify (and perhaps modify) cognitive/affective mechanisms of adherence behavior in patients at high risk for ACS recurrence and mortality. Physicians routinely magnify patients' FoR after acute life-threatening medical events to capitalize on the "teachable moment." This study may provide evidence for the opposite approach, as well as validated measures to assess FoR in CVD patients.

2. Study Design

We will enroll 100 English- and Spanish-speaking patients (50 intervention group, 50 control group) who recently presented to the ED of the New York Presbyterian Hospital (NYPH) with a probable admitting diagnosis of acute coronary syndrome (ACS).

Specifically, eligible participants will be patients already enrolled in a separate approved protocol (IRB-AAAR7350: "Testing biopsychosocial mechanisms of the posthospital syndrome [PHS] model of early rehospitalization in cardiac patients") who presented to the NYPH ED with chest pain and an admitting diagnosis of non-ST-elevation myocardial infarction (NSTEMI) or unstable angina (UA). Prior to enrollment in that separate study, participants will have verbally confirmed with the caregiving physician that they were not active substance abusers, demented, and/or psychotic. Patients will *not* be eligible for the present study unless they indicated during the consent procedure for that separate protocol that they were willing to be contacted about participating in a different study. In terms of timing, patients who consented to the PHS study within the last 6 weeks (i.e., 42 days) will be potentially eligible for the present study.

The fundamental components of the study design are described below (see Procedure section for more details). One to three bilingual (English/Spanish) research assistants (RAs) assist in data collection at each session.

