Study recruitment occurs primarily in the hospital after the potentially eligible patients (those currently enrolled in the separate protocol AAAR7350 and interested in learning more about other research studies) have been admitted to the hospital and transferred to an inpatient bed. For some patients, study recruitment may occur post-discharge, up to 6 weeks following participants' presentation to the Emergency Department when they enrolled in the PHS study. Research coordinators for the present protocol will approach these patients, introduce the study and begin the informed consent process. Consenting participants are randomized to the intervention or control condition and complete baseline measures for the present protocol at the pre-training session (i.e., Time 1). Participants are given an electronic tablet device and a brief training on its use at the end of or within several days of this baseline session. For the subset of patients who provide signed consent and the brief tablet training for this intervention study in the hospital but who are then discharged prior to this session, the Time-1 session is conducted by phone while the patients are at home. An additional subset of patients who consent to participate in this study will come to CUMC after hospital discharge to conduct the questionnaires and the brief tablet training of the pre-training session (i.e., Time 1) in person. All participants then complete 8 sessions of the training (intervention or control version) at home twice per week for 4 weeks using the tablet. During this time their adherence to a heart medication is monitored using eCAP devices that they receive during enrollment or in the mail. For participants currently prescribed aspirin but no other heart medication, their adherence to aspirin will be monitored using the eCAP devices. For participants *not* currently prescribed aspirin but who *are* currently prescribed a heart medication other than aspirin, such as a non-aspirin antiplatelet, a beta-blocker, a statin, or an antihypertensive medication, their adherence to this other heart medication is monitored using the eCAP devices. Within several days following the completion of the 4-week training, participants are then contacted by phone for the post-training session (i.e., Time 2), during which they complete the same measures as completed at the Time-1 session. Then, participants return the tablet devices to CUMC researchers using pre-addressed envelopes/packages mailed to their homes. Finally, at 8 weeks after the Time-1 session, participants return the eCAP medication adherence monitoring devices to CUMC researchers also using pre-addressed envelopes/packages boxes.

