Control version: For participants in the control group, in the 130 training trials of the task, the location of the target letter (i.e., top or bottom) is equally likely to be the location previously occupied by the threat-related word and the neutral word. The 30 test trials for the control group are identical to the test trials for the intervention. Example trial from intervention group (see above). Thus, participants in the control group are not reinforced for attending to either particular kind of stimuli. For each administration of the task, preferential attentional allocation toward threat-related information is assessed as the mean response time for test trials in which the target location is congruent with the threat-related word subtracted from the mean response time for test trials in which the target location is incongruent with the threat-related word. In this way, as a manipulation check, we will assess the extent to which attentional allocation to threat diminishes as a function of group and session (1-8) over the course of the 8 training sessions.

Cognitive bias modification for interpretation (CBM-I)

Intervention version: CBM-I trials are designed to train participants to appraise ambiguous information that is potentially related to ACS threat as benign. Each of 100 trials begins with a word or short phrase corresponding to either a threatening (e.g., “dying”) or benign (e.g., “sleep”) interpretation of a sentence that follows it (e.g., “You have been waking up tired recently”). On the next screen participants are asked to tap one of two buttons on the screen of the tablet to indicate “Yes” or “No” in response to the question “Was the word or phrase related to the sentence?” Participants in the intervention group receive positive feedback (“You are correct!”) for rejected threat interpretations or for benign interpretations, and otherwise they receive negative feedback (“You are incorrect”).

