We will test this mediational hypothesis using conditional process modeling with the PROCESS macro in SPSS.²¹ Although we will likely have insufficient power to test the question definitively, the results will inform whether a future larger trial is warranted. The behavioral outcome in the model is heart medication adherence from the eCAP data: mean proportion of adherent days in the 2-month monitoring period that occurs within several months after hospital discharge. The predictor is group (intervention, control). The mediator is pre-to-post change in FoR from Time 1 to 2. For a secondary analysis, we will test the outcome as the magnitude of the slope of change in weekly proportion of adherent days during the 2 months. We will evaluate whether there is a significant indirect effect that supports the notion that the intervention vs. the control training engaged the target mechanism in such a way that changes in the target predicted improved heart medication adherence over the month-long intervention.

Exploratory Aim 1.

We will test for off-target intervention effects on future time perspective, as well as the alternative mediation path through improvement in future time perspective.

The test will be structured as for Specific Aim 3 but with pre-to-post change in future time perspective as the tested mediator.

Exploratory Aim 2.

We will test whether the intervention is associated with greater increases in physical activity relative to the control group and whether this association is mediated by changes in FoR or future time perspective.

The test will be structured as for Specific Aim 3 and Exploratory Aim 1 but with physical activity as the tested behavioral outcome measure instead of medication adherence.

Power analysis.

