In prior research with $N = 97$ at Time 1 using a similar intervention in cancer patients, a moderate effect size (Hedges $g = 0.54$) was found for differences in FoR between the intervention ($n = 64$) and control ($n = 36$) groups after 3 months and a somewhat smaller effect size (Hedge's $g = 0.35$) immediately after the 1-month intervention.¹³ Using G*Power 3.1,²² we tested a range of effect sizes for two levels of power. We determined that the present study is conservatively powered to change FoR in a fixed-effects one-way ANOVA with an effect size f of 0.35 or larger with a sample size of $N = 100$ (50 intervention, 50 control), given alpha = .05 and an intention-to-treat design in which missing data due to attrition are handled with multiple imputation.

4. Study Procedures

Patients will be considered for enrollment in the present study who are currently enrolled in AAAR7350 (the PHS study), who signed consent for AAAR7350 within the last 6 weeks (i.e., 42 days), who have indicated they are willing to hear about other research studies, and who have an Elevated Threat Perception score. Consent will be obtained using an IRB-approved consent form.

Pre-training/Time 1: For patients consenting to the study in the hospital, the pre-training session ideally occurs at this same visit. The RA will assess the potential mechanisms of behavior change verbally. At the end of this session, each patient will be given a tablet and an eCAP bottle with a brief explanation of their use. The estimated duration of this session is 45 minutes, including the consent process, questionnaires, and the brief training in the use of the tablet. A subset of patients will complete the consent process and receive the devices (eCAP bottle, tablet) with a brief training in the hospital and will then separately complete the questionnaires verbally by phone within several days. A separate subset of patients will complete the Time-1 session at CUMC sometime after hospital discharge but before 6 weeks (i.e., 42 days) have elapsed from the time of consent to the protocol AAAR7350.

Training phase: Random group assignment to the intervention or control group will be determined in a double-blind way by the programmed tasks on the tablet for each participant.

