Participants are asked to complete 8 at-home 30-minute intervention sessions (both CBM-A and CBM-I tasks are programmed to occur sequentially in one session). The schedule of sessions is 2 times per week. Participants will receive brief, automated text messages 2 times each week reminding them to complete these sessions. Phone calls will be conducted instead of text messages for participants without text message capability or for particular scheduled training sessions when participants do not respond to the text reminders.

Post-training/Time 2: A clinical coordinator will administer the measures by phone interview. Participants who prefer a home visit may complete the session in person and return their tablet to the interviewing clinical coordinator at that time. The estimated duration of this session is 45 minutes. All other participants will return their tablets and eCAP bottles via mail: one pre-addressed envelope/ package for the return of the tablet at 4 weeks after the Time-1 session and soon after completion of the Time-2 session and one separate pre-addressed envelope/package for the return of the eCAP bottle at 8 weeks after the Time-1 session.

Monetary compensation is administered via pay card in two installments. In the first installment of monetary compensation, participants receive \$20 at Time 1. Regarding the second installment of monetary compensation, it is structured such that participants are incentivized to return their devices with complete data. They receive \$5 for completing the 1st at-home tablet tasks session, \$5 for the 2nd, \$5 for the 3rd, \$5 for the 4th, \$10 for the 5th, \$10 for the 6th, \$20 for the 7th, and \$20 for the 8th tablet tasks session. They receive \$20 for completing the Time 2 interview. The second study compensation is contingent upon return of the tablet following Time 2. Finally, in the third study compensation, participants receive \$20 for returning the eCAP device. Thus, total study compensation for participants who complete all sessions is \$140 (\$20 in first installment + up to \$100 in second installment + \$20 in third installment).

References

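### Does measuring test-retest reliability across the training period undermine Aim 1's reliability evidence for fear of recurrence?

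*Combined protocol and SAP*

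**What the plan says.** Section 3, Specific Aim 1, lists three checks on the mechanism measures: correlations between FoR and future time perspective at Time 1, correlations of FoR with threat perception and adherence, and stability over time. On the third it says "we will also assess test-retest reliability from Time 1 to 2, both across and within groups". It then concludes: "In this way we will ensure that we have valid and reliable measures of our proposed mechanisms of behavior change". It does not name the coefficient, set a threshold, or say which of the pooled, intervention-arm and control-arm values answers the reliability question.

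Section 2 places the training between the two measurements: "All participants then complete 8 sessions of the training (intervention or control version) at home twice per week for 4 weeks using the tablet". Of the control attention task it says that "participants in the control group are not reinforced for attending to either particular kind of stimuli". Future time perspective is expected to move only under Exploratory Aim 1: "We will test for off-target intervention effects on future time perspective". Section 1 mentions "validated measures to assess FoR in CVD patients" as something the study may provide.

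**The concern.** A test-retest coefficient measures reliability only if the construct is left alone between the two occasions. Here one arm receives training designed to change it. A fall in FoR, and above all a fall that differs between patients, lowers agreement between Time 1 and Time 2 even if the scale measures without error. On that reading the more the intervention succeeds, the less reliable the scale may appear in the treated arm.

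The FoR scale was built for breast cancer and newly adapted for cardiac patients, so later users may rely on the coefficient reported here. With three unranked values and no named statistic, the pooled figure could be quoted as the scale's reliability. For future time perspective the same worry arises only if the off-target effect is real.

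**Working it through.** The plan states no reliability figure, so there is none to reproduce. The check asks how far the pooled and intervention-arm values could drift from the control-arm value.

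**Inputs from the documents.** There are 50 patients per arm. The prior cancer study gave a standardised effect of 0.35 immediately after a one-month intervention and 0.54 at three months (Specific Aim 2 and Power analysis). The trial is powered for an effect "with an effect size f of 0.35 or larger", which for two equal arms is d = 2 × 0.35 = 0.70.

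**Assumptions, not in the documents.** True four-week stability r is 0.80 (0.70 as a check). The between-patient SD of response, s, is 0 to 0.5 baseline SDs and independent of baseline.

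**Model.** Time 1 variance is 1. Control-arm Time 2 variance is 1, with correlation r. Intervention-arm Time 2 is lowered by a mean d with SD s.

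- Intervention arm: Pearson = r/√(1 + s²); absolute-agreement ICC = 2r/(2 + s² + d²).
- Pooled 1:1: V₂ = 1 + s²/2 + d²/4; Pearson = r/√V₂; ICC = 2r/(1 + V₂ + d²/4).

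**Worked case, r = 0.80, d = 0.35, s = 0.** d² = 0.1225 and d²/4 = 0.0306, so V₂ = 1.0306.

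- Pooled Pearson = 0.80/√1.0306 = 0.788.
- Pooled ICC = 1.60/2.0613 = 0.776.
- Intervention-arm Pearson = 0.800.
- Intervention-arm ICC = 1.60/2.1225 = 0.754.

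**Other cases at r = 0.80.** The control arm is 0.80 by assumption throughout.

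| d | s | Intervention Pearson | Intervention ICC | Pooled Pearson | Pooled ICC |
|---|---|---|---|---|---|
| 0.35 | 0 | 0.800 | 0.754 | 0.788 | 0.776 |
| 0.35 | 0.5 | 0.716 | 0.674 | 0.744 | 0.732 |
| 0.54 | 0 | 0.800 | 0.698 | 0.772 | 0.746 |
| 0.70 | 0 | 0.800 | 0.643 | 0.755 | 0.713 |

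At r = 0.70, d = 0.35, s = 0, the pooled Pearson is 0.690, the pooled ICC 0.679 and the intervention-arm ICC 0.660.

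**Sampling error for comparison.** Fisher's z at r = 0.80 is 1.0986. The half-width is 1.96/√97 = 0.199 for n = 100, giving 0.72 to 0.86, and 1.96/√47 = 0.286 for n = 50, giving 0.67 to 0.88.

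**Bias against precision.** In simulation at r = 0.80, d = 0.35, s = 0, the pooled Pearson averages about 0.786. Its root mean squared error is about 0.04, against about 0.05 for the control arm alone. For the agreement ICC both are about 0.05, with the pooled value slightly better. The order reverses when response varies widely: at s = 0.5 the pooled Pearson's bias alone is 0.800 − 0.744 = 0.056, about equal to the control arm's whole error.

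**The case for a change.** The strongest case for a change is that it costs a sentence. The plan confines its FoR and future time perspective correlation to pre-intervention data but gives reliability no such protection. Leaving both the coefficient and the lead value open means that the choice may be made after the data are seen. If an agreement ICC is chosen and response varies, the intervention-arm value could fall from 0.80 to 0.67.

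The facts in this argument stand: the interval contains the training, and the coefficient is not named. The larger figures carry less weight. The effect of 0.54 was seen at three months, whereas Time 2 follows within days of the four-week training. The value 0.70 is the size the study is powered to detect, not one it expects. The agreement ICC appears nowhere in the documents; the only statistic named among the Aim 1 checks is a zero-order correlation. The loss from varying response assumes that response is unrelated to baseline. If patients instead fell in proportion to their starting score, the intervention-arm correlation would stay at 0.80.

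Nor is the control arm a clean retest. Its patients also see threat words and receive mixed feedback over eight sessions, and FoR may change naturally after a suspected cardiac event. Interview mode can differ too: Time 1 may be in person, while for Time 2 "A clinical coordinator will administer the measures by phone interview" in most cases. Relying on that arm alone also widens the interval to 0.67 to 0.88, before any attrition.

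**Conclusion.** The observation is correct, but it does not call for a change. The plan already produces the control-arm coefficient beside the other two, so a reader can see whether training disturbed stability. An analyst can sensibly lead with the control arm, name the coefficient, and describe the result as four-week stability.

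At the only cited effect that matches the timing (0.35, uniform response, assumed stability 0.80), the pooled loss is 0.012 for a correlation and 0.024 for an agreement ICC. The intervention-arm loss is zero and 0.046 respectively. Apart from the intervention-arm ICC, these are well inside the sampling error, and under this model any bias makes the scale look less reliable than it is. In that case restricting the estimate to the control arm would not improve accuracy; it would do so only if individual response varied widely, which the documents give no means of judging. No conclusion in Aims 2 or 3 depends on the point.
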